Appendix

eMethods

Development of the EMA's proposed key information section with qualitative statements

The EMA published its proposal for a key information section in patient leaflets in July 2024.⁹ The content of this proposed section was based on surveys conducted with patients, members of the public, and healthcare professionals, focusing on what they considered to be 'key information' about a medicine. According to the EMA's draft, the key information section should include: the indication and goal of treatment / main benefits (with cross reference to section 1 of the current patient leaflet), contraindications and important precautions (section 2), and most serious side effects / main risks (section 4).

Since the guidance and template for the EMA's proposed key information section had not been finalized by the time of the trial, we developed a version for testing based on the content of the EMA's draft proposal. Statements about the goal of treatment, benefits, contraindications, and side effects were sourced from the EMA's medicines overview and patient information leaflet. To ensure the accuracy of the version used in the trial, we shared our draft with the EMA and incorporated their feedback into the final version tested.

Development of the key information section with qualitative and quantitative information

We designed the key information section that includes both qualitative and quantitative information based on evidence-based principles for communicating health information to patients and members of the public. Patients need information about the benefits, harms, and uncertainties of drugs in order to make informed decisions consistent with their preferences. This includes qualitative descriptions of the intention of treatment (e.g., whether it is palliative or curative),¹⁷ and quantitative data on the effect of treatment on clinically meaningful outcomes.¹⁵ Presenting this information in a structured format helps support better comprehension.^{10,13}

We based the design of the key information section on the Drug Facts Box – a tabular summary format developed to communicate drug benefits and harms to the public.¹³ We adapted the design considerably to align with the EMA's consultation on the proposed key information section and to address gaps in the presentation of prescription drug information in current European patient leaflets.

The key information section that includes both qualitative and quantitative information on drug benefits and harms is divided into 2 parts: general information about the drug, and data on treatment outcomes. The general information section begins with a header describing the drug name and approved indication ("Key information about..."), followed by 2 subheadings. The first subheading ("What is Fotivda and what is it used for") includes 3 bullet points.

The first bullet point describes the indication of the drug as approved by the EMA. The second describes the intention of treatment, indicating whether treatment is curative or is intended to delay disease progression and extend survival. The third bullet summarizes the main benefits demonstrated in clinical trials, including whether the drug was associated with clinically relevant outcomes for patients. This section concludes with another subheading which summarizes the key features of the clinical trial which supported the drug's approval ("Benefits and side effects of Fotivda"). A brief sentence provides information about the comparator treatment used in the clinical trial and the number of participants enrolled.

Next, the key information section presents data on treatment outcomes in a tabular format. The columns correspond to the treatments administered in the clinical trial and the rows correspond to the outcomes measured. For each outcome, the table displays the absolute

difference between the two treatments; the results for the new drug; and results for the comparator treatment.

To present information on drug benefits, we included data on outcomes that are clinically meaningful for patients with the condition, as well as the primary outcome of the clinical trial that supported the drug's approval. In oncology trials, clinical outcomes typically include overall survival and quality of life. Therefore, if the trial's primary outcome was a surrogate endpoint (e.g., progression-free survival), the included 3 rows of benefit information: overall survival, quality of life, and the surrogate endpoint. If the primary outcome was overall survival, only 2 rows were included: overall survival and quality of life.

For tivozanib, the primary endpoint of the pivotal study was progression-free survival. To reduce confusion with overall survival, we described progression-free survival in plain language as "*how long did people have before the cancer grew or spread*", while overall survival was described as "*how long did people live?*".¹⁸ Because the improvement in overall survival was not statistically significant between tivozanib and sorafenib at the time of approval, we reported the absolute difference between the two treatment in the corresponding column of the table but noted that the observed difference may be due to chance.

For data on quality of life, we used any measure of global health-related quality of life reported in the EPAR, given that quality of life outcomes are inconsistently measured and reported in cancer drug trials.¹⁹ In the case of tivozanib, quality of life was measured using a 108-point scale. Because the difference in quality of life between tivozanib and sorafenib was not statistically significant, we reported the absolute difference in the table but noted that the observed difference may be due to chance.

The final outcome reported in the table is the percentage of patients who experienced severe side effects. Severe side effects were defined as grade 3 (severe events requiring hospitalization or prolongation of hospitalization) and grade 4 (life threatening) adverse events, according to the common terminology criteria for adverse events (CTCAE). We reported the overall proportion of patients who experienced these adverse events rather than the proportion determined to be treatment related by trial investigators. We excluded grade 5 adverse events (death) since these were relatively rare and could be misinterpreted.

Drug information

Tivozanib (Fotivda) was approved by the EMA in 2017 for the treatment of advanced kidney cancer. The primary outcome of the clinical trial that supported tivozanib's approval showed an additional benefit in progression-free survival of 2.8 months compared to sorafenib (11.8 months vs 9.1 months). Overall survival and overall health related quality of life were secondary outcomes in the trial but neither showed a statistically significant difference between the two treatments. Severe harms (defined as life threatening or requiring hospitalization [grade 3 and 4]) were more common with tivozanib (70%) than with sorafenib (64%).

References

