To evaluate the impact of structured benefit-harm information in patient leaflets, we will conduct a randomized controlled trial with a nationally representative sample of adults in the United Kingdom (UK). The trial will evaluate whether including qualitative or quantitative information about drug benefits and harms improves individuals' expectations and understanding of a newly approved drug. Participants will be randomly assigned to one of three groups: (1) the standard patient information leaflet (control), (2) a leaflet incorporating the EMA's proposed key information section with qualitative statements, or (3) a leaflet with a key information section that includes both qualitative and quantitative information on the drug's benefits and harms.

Methods

This study received ethics approval from the London School of Economics and Political Science. The protocol was registered prior to recruiting participants (ClinicalTrials.gov) and the study will be reported in accordance with the CONSORT guidelines for randomized controlled trials.

Randomization

Participants will be individually randomized with equal allocation to 1 of 3 versions of a patient information leaflet: (1) the standard patient information leaflet (control), (2) a leaflet incorporating the EMA's proposed key information section with qualitative statements, or (3) a leaflet featuring a key information section that summarises quantitative data on the drug's main benefits and harms in addition to qualitative statements. We will use Qualtrics to randomize participants and to administer the survey.

Participants

Adults 18 years and older, fluent in English, and residing in the UK will be invited to participate in this survey. Participants will be recruited by Cint, a market research company that identifies participants from hundreds of research panel providers that use different methods for recruitment. We plan to recruit a nationally representative census-matched sample of adults according to age, sex, and education. Informed consent will be obtained from participants before initiating the survey; participants will be directly compensated by the survey company after completion. No identifying information about participants will be recorded.

Interventions

Participants in the control group will receive the standard patient information leaflet for a recently approved cancer drug, obtained electronically from the EMA website. There are 2 experimental conditions.

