For participants randomized to receive the EMA's proposed key information section with qualitative statements, we developed a version based on the draft proposal published by the EMA.⁹ The proposed key information section summarizes the goal of treatment, main benefits, contraindications, and most serious side effects. To ensure accuracy of our interpretation, we sought feedback from the EMA. The final version tested in the trial incorporated their suggestions.

Next, we developed a key information section that includes quantitative data on the drug's main benefits and side effects, modeled on the Drug Facts Box – a tabular summary format for prescription drugs, designed to resemble a nutrition label.¹³ The key information section presents qualitative information about the drug (including its indication and treatment goal), and how it was studied (the comparator treatment and number of patients enrolled in the clinical trial that supported the drug's approval). It supplements this with quantitative data the drug's benefits and side effects. Data on the drug's benefits and side effects were sourced from European Public Assessment Reports (EPARs). Further details are provided in the appendix.

Procedure

Upon entering the study, participants will be randomized to 1 of 3 versions of a patient leaflet. The patient leaflet is for tivozanib (Fotivda), a cancer drug approved by the EMA for the treatment of advanced kidney cancer. An electronic version of the patient leaflet along with a download link will be displayed alongside each multiple-choice question. Participants will first complete a practice question designed to test their ability to scroll through and navigate the leaflet. Participants who answer the practice question incorrectly will be excluded from the study at this stage.

The first set of questions is designed to evaluate participants' expectations, perceived magnitude, and understanding of the drug's benefits and side effects based on the information provided in the patient leaflet. To assess expectations, we will ask participants about the likelihood that patients with advanced kidney cancer would be cured, live longer, or

feel better if they were treated with tivozanib. They will also be asked about the perceived magnitude of the tivozanib's benefits and side effects.^{13–15}

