- Fotivda may increase how long people live without their disease getting worse. However, it does not cure advanced kidney cancer.

For further information about Fotivda and its uses, see section 1.

What you need to know before you take Fotivda

- Do not take Fotivda if you are allergic to the active ingredient, tivozanib, or if you are taking St. John's Wort (a herbal remedy for depression).
- Talk to your doctor if you have high blood pressure, have had an aneurysm (a bulge in a blood vessel), have had blood clots or have any of the signs or symptoms of heart failure.

For further information, see section 2.

Most important side effects with Fotivda

- The most common side effect with Fotivda is high blood pressure (which occurs in almost half of patients and can be serious in a quarter of patients).
- Other common side effects are voice changes, tiredness and diarrhoea (which occur in about a quarter of patients).

For the full list of possible side effects, see section 4.

To understand all information about using this medicine, it is very important that you read the rest of this leaflet.

Key information about Fotivda for renal cell carcinoma (kidney cancer)

What is Fotivda and what is it used for:

- Fotivda (tivozanib) is a medicine to treat adults with advanced kidney cancer that has come back after previous treatment or has spread to another part of the body.
- Fotivda does not cure advanced kidney cancer.
- Fotivda may increase the time until a test shows the cancer has grown or spread, but it has not been shown to extend how long people live.

Benefits and side effects of Fotivda:
 In a study involving 517 people, Fotivda was compared to sorafenib, a standard treatment for kidney cancer. What difference did Fotivda make?

	Fotivda	Standard treatment
How long did people live?	People given Fotivda lived 2.6 months less . However, this finding may be due to chance.	28.2 months vs 30.8 months
How did people feel?	People given Fotivda felt 1.1 points worse on a 108-point scale. However, this finding may be due to chance	4.8 points worse vs 3.7 points worse
How long did people have before the cancer grew or spread?	People given Fotivda had 2.8 months longer before the cancer grew or spread.	11.9 months vs 9.1 months
How common were serious side effects?	People given Fotivda had 6% fewer serious side effects (disabling, life-threatening, or requiring hospitalization).	64% vs 70%

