- 2.6 months **less** than people given standard treatment **[correct]**
- About the same as people given standard treatment
- 2.6 months **longer** than people given standard treatment
- 6 months **longer** than people given standard treatment
- Not sure

----- end of page-----

9. Overall, how large are the benefits of Fotivda?

- Very large
- Large
- Moderate
- Small
- Very small to none

----- end of page-----

10. To confirm that the survey is functioning correctly, please select 'Standard treatment', below.

- Fotivda
- Advanced kidney cancer
- Standard treatment **[correct]**
- Neither Fotivda or standard treatment

----- end of page-----

11. Compared to standard treatment, how common were serious side effects with Fotivda? **[Key information table group]**

- 22% **less** common than with standard treatment
- 6% **less** common than with standard treatment **[correct]**
- About the same as standard treatment
- 6% **more** common than with standard treatment
- 22% **more** common than with standard treatment
- Not sure

----- end of page-----

12. What is the most common serious side effect of Fotivda?

- Rapid or irregular heart beat
- High blood pressure **[correct]**

- Diarrhoea
- Muscle spasms
- Not sure

----- end of page-----

13. How concerning are the side effects of Fotivda?

- Extremely concerning
- Very concerning
- Somewhat concerning
- Not at all concerning

----- end of page-----

14. Do you think the benefits of Fotivda outweigh the side effects?

- Definitely yes
- Probably yes
- Probably no
- Definitely no

----- end of page-----

15. What is the recommended dose of Fotivda during the first 3 weeks of treatment? **[All groups]**

- One 890 microgram capsule daily
- One 1340 microgram capsule daily **[correct; answer in section 3 of PIL]**
- Two 1340 microgram capsules daily
- Two 890 microgram capsules daily
- Not sure

----- end of page-----

Section C: Participants' satisfaction with the patient leaflet

You're almost done. What was your experience of using the patient leaflet for Fotivda?

16. Was it easy to find information about Fotivda using the leaflet?

- Very easy
- Easy
- Difficult
- Very difficult

17. Was it easy to understand the information?

- Very easy
- Easy
- Difficult
- Very difficult

Please rate your agreement with the following statements.

18. The leaflet helped me think about the benefits of Fotivda.

- Strongly agree
- Agree
- Disagree
- Strongly disagree

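### The appendix and the table shown to participants give opposite directions for severe harms with tivozanib (70% vs 64% against 64% vs 70%), and the question 11 answer key follows the table

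*Combined protocol and SAP*

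**What the plan says.** Three places state how common severe harms were with tivozanib compared with sorafenib.

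- **Appendix, Drug information:** severe harms, defined there as grade 3 and 4, "were more common with tivozanib (70%) than with sorafenib (64"%).
- **Figure 1, table in the key information section with qualitative and quantitative information:** "People given Fotivda had 6% fewer serious side effects (disabling, life-threatening, or requiring hospitalization"), with 64% vs 70% beside it. Fotivda is the first treatment column and standard treatment the second.
- **Survey Section B, question 11** (asked only of the table group): the keyed answer is "6% less common than with standard treatment [correct"].

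Three further statements show that these should agree. The appendix describes the table's harm row thus: "The final outcome reported in the table is the percentage of patients who experienced severe side effects", and defines these as grade 3 and 4 events from any cause. It gives the content of each row as the absolute "difference between the two treatments; the results for the new drug; and results for the comparator treatment". The Interventions section says that data on the drug's "benefits and side effects were sourced from European Public Assessment Reports (EPARs").

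The same appendix paragraph also reports a benefit in "progression-free survival of 2.8 months compared to sorafenib (11.8 months vs 9.1 months"), whereas the Figure 1 table gives 11.9 vs 9.1 months.

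**The concern.** The two percentages are the same, but they are attached to opposite treatments. This matters more than a slip in background text would, because the table is what one randomised arm receives. The stated aim is "To evaluate the impact of structured benefit-harm information in patient leaflets", and that aim presupposes that the information is accurate.

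**If the table is reversed:**
- The quantitative arm is told that the drug has fewer severe harms than its comparator when it has more. The leaflet is displayed beside each multiple-choice question. Unlike the survival and quality-of-life rows, the harm row has no caveat about chance, so it reads as a firm finding.
- Question 11 credits a statement that is false about the drug.
- Two of the perceived-magnitude comparisons under Secondary outcomes are exposed: side effects not concerning (question 13) and benefits outweighing side effects (question 14). Any contrast with the quantitative arm would reflect wrong content rather than the format and accurate data that the trial sets out to test. Analysis after fielding could not repair that.

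**If the appendix is reversed:** the protocol's description of the drug is wrong and the trial data are unaffected.

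**Working it through.** **1. Differences, tivozanib minus sorafenib**

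| Source | Tivozanib | Sorafenib | Difference | Direction in words |
|---|---|---|---|---|
| Appendix, Drug information | 70% | 64% | 70 − 64 = +6 points | more common |
| Figure 1 table | 64% | 70% | 64 − 70 = −6 points | 6% fewer |
| Question 11 key | – | – | −6 points | 6% less common |

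Each subtraction is correct on its own. The conflict is over which treatment has which percentage, and the signed differences are 6 − (−6) = 12 points apart.

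**2. Could the table's columns have been read in the wrong order?** No. The other three rows match their own wording only with Fotivda first:

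- overall survival: 28.2 − 30.8 = −2.6 months (worded as 2.6 months less);
- quality of life: −4.8 − (−3.7) = −1.1 points (worded as 1.1 points worse);
- progression-free survival: 11.9 − 9.1 = +2.8 months (worded as 2.8 months longer).

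Direction is also given in words in the appendix, the table and the key, so a table broken in PDF extraction would not explain the conflict.

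**3. Could the outcomes or comparators differ?** No. The appendix defines the table's harm row as grade 3 and 4 events, the same grades as in the Drug information paragraph. The table says serious and adds disabling events where the appendix says severe, but the pair of percentages is identical. The text above the table names sorafenib as the standard treatment.

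**4. Could rounding explain it?** No. If the percentages are rounded to whole numbers:

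- appendix: lowest 69.5 − 64.5 = +5, highest 70.5 − 63.5 = +7;
- table: lowest 63.5 − 70.5 = −7, highest 64.5 − 69.5 = −5.

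The ranges do not overlap.

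**5. The smaller mismatch, progression-free survival.** Plain subtraction of the appendix figures gives 11.8 − 9.1 = 2.7, not the stated 2.8. With one-decimal rounding:

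- 11.8 vs 9.1 allows 11.75 − 9.15 = 2.60 up to 11.85 − 9.05 = 2.80;
- 11.9 vs 9.1 allows 11.85 − 9.15 = 2.70 up to 11.95 − 9.05 = 2.90.

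A reported 2.8 covers 2.75 to 2.85 and is possible under both. The discrepancy is the 0.1 month between 11.8 and 11.9.

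**6. What the harm row reaches.** The primary outcome uses questions 5 to 7 (cure, survival, feeling better), and the sample size calculation does not use the harm figures. Neither the control leaflet nor the qualitative section carries this row, so the comparison of those two arms is untouched. What remains is question 11 in the quantitative arm, and that arm's results on questions 13 and 14.

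**The case against.** The contradiction itself cannot be argued away. The case on the other side concerns its weight, and it has three parts.

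*The damage is conditional and limited.* It arises only if the table is the reversed version, and even then it spares the primary outcome. Question 11 goes to one arm only, so there is no between-arm contrast to bias. Participants are told to answer from the leaflet, so the question would still measure reading. Questions 13 and 14 are secondary and name no comparator. All of this stands, and so does the fact that no effect on them can be sized from the documents.

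*The documents lean towards the table.* Its wording, percentages and answer key agree with one another. The appendix narrative looks less careful elsewhere: it calls the overall survival difference an improvement, while the table has tivozanib patients living 2.6 months less. Its progression-free survival figure also fits the 2.8-month difference less well. If unrounded values are assumed uniform within their rounding intervals, the difference rounds to 2.8 with probability 0.125 for 11.8 vs 9.1 and 0.75 for 11.9 vs 9.1. These are fair hints that the harmless branch may be the true one, but they do not settle the harm figures. The key was written to match the table, so it is not independent confirmation, and carelessness over one figure does not establish an error in another.

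*The progression-free survival mismatch is trivial.* Agreed. It is 0.1 month, no survey question scores it, and it adds nothing to the seriousness of the main point.

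**Conclusion.** The concern holds. The plan gives the difference in severe harms as +6 points in the appendix (+5 to +7 allowing for rounding) and −6 points in the table and answer key (−7 to −5). The tivozanib figure is either 70% or 64%. One version is reversed, and the documents do not show which.

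This rests on two readings that the plan itself supplies: the table's harm row is the same grade 3 and 4 outcome as in the Drug information paragraph, and the first treatment column is Fotivda. The rounding ranges assume conventional rounding to whole percentages.

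The point must be fixed because the serious branch has not been excluded and it concerns what about 700 planned participants (the target per group) are shown. It does not threaten the primary analysis or the sample size.

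**What to change.** Before fielding:

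1. Check both harm percentages and the treatment each belongs to against the EPAR, the source that the protocol names.
2. Make the Drug information paragraph, the table row (wording and percentages) and the question 11 key agree. If the table stands, only the appendix sentence changes. If the appendix stands, both the table row and the key change.
3. At the same check, reconcile the progression-free survival figure (11.8 or 11.9 months).

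If fielding has begun, report which version participants saw. If it was the wrong one, say so wherever the quantitative arm's results on questions 11, 13 and 14 are presented. Interpret question 11 as reading of the leaflet only, and questions 13 and 14 as responses to inaccurate harm content.

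The cost is one source check and a few words in the appendix, or in the table row and answer key. No extra participants are needed.
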